3.4 Adaptive design

This study incorporates the use of an adaptive design. Study specific adaptive features and their limits are described in Table 6.

Adaptive features may be implemented only with the approval of the Sponsor. Implementation of adaptive features affecting whole treatment, or the entire study, will be documented in a non-substantial amendment.

The exceptions to this are those adaptive features in Table 6 that relate to individual participant safety. These may be implemented at the discretion of the Investigator and recorded in that participant's source data.

Table 6: Adaptive protocol features

Adaptive Study Design Areas	Features	Limits
Replacement of withdrawn participants	
1. Withdrawn participants can be replaced at the discretion of the Sponsor and the Investigator. The replacement participant(s) will be enrolled into the same treatment group as the original participant(s). Evaluable data from the withdrawn participant will be included in the analysis as appropriate.2. Replacement participants may be enrolled in an ongoing treatment group, dosed together as a group or dosed separately.	
I. Study-specific AR rules apply (section 4.3)

Adaptive Study Design Areas	Features	Limits
Samples and Assessments (safety)	
1. Additional safety assessments may be performed on an individual participant if it is considered clinically necessary by the Investigator for individuals on a case-by-case basis.2. Additional safety assessments (including but not limited to laboratory safety samples, vital signs and ECGs) may be added to the Schedule of Assessments at additional time-points for an upcoming treatment group if necessary from a safety/tolerability perspective, on the basis of evolving data.3. Additional safety assessments may refer to either:
a. an increased number of the same safety assessments planned in the existing Schedule of Assessments.b. additional parameters (specific tests) on assessments already scheduled e.g., troponin tests on safety blood samples.c. additional safety tests requiring additional blood/urine sample collections or other clinical procedures e.g., ultrasound scans.4. Specialist referrals (e.g., to a cardiologist) may be made (and may include all relevant assessments and investigations) if it is considered clinically necessary by the Principal Investigator (PI), Sponsor or Safety Review Committee (SRC) for individuals on a case-by-case basis.5. The timing of safety assessments including but not limited to laboratory safety samples, vital signs and ECGs may be adjusted in accordance with evolving data and dosing schedule.	
I. The maximum blood volume for scheduled assessments is given in Section 7.14. This maximum may only be exceeded if additional unscheduled blood samples/ investigations are performed as necessary to ensure the safety of the individual participants.II. If additional time points for safety assessments are required for upcoming participants in specified treatment groups, this will be documented in a non-substantial amendment, providing the overall risk profile of UPB-101 has not changed.III. If additional safety assessments or parameters are required for upcoming participants in specified treatment groups and have a similar risk profile to those planned in this study protocol, they will be documented in a non-substantial amendment. Additional safety assessments required for upcoming participants in specified treatment groups that are more invasive or have a different risk profile to those in this current protocol must be detailed in a substantial amendment.IV. If there are no clinically significant findings in safety assessments up to Day 85, further follow-up can be discontinued.V. A maximum number of specialist referrals for individuals will be determined on a case-by-case basis and cannot be pre-defined as investigations will be performed as necessary to ensure the safety of the individual participants.

Adaptive Study Design Areas	Features	Limits
Samples and assessments (PK)	
1. Samples will be collected at timepoints detailed in the Schedule of Assessments and will be processed and stored as detailed in the Laboratory Manual.
	
I. Follow Schedule of Assessments and max blood volume will not be exceeded.
 
II. Analysis of PK samples taken between Day 9 and Day 14 is optional at the Sponsor's discretion (which may or may not be reported as part of this study).

Samples and assessments (PD)	
1. Specific PD biomarkers for exploratory analysis will be selected based on relevant data from ongoing clinical studies.
	
I. Follow Schedule of Assessments and max blood volume will not be exceeded.

In-house duration and visit numbers	
1. The in-house stay or follow-up period may be prolonged if:
 
 a. it is considered clinically necessary to prolong the in-house stay by the PI/delegate for individuals on a case-by-case basis b. the SRC considers it necessary from a safety/tolerability point 
2. The follow-up period for a dose treatment group may be prolonged if evolving safety and tolerability data requires a longer or shorter follow-up period.
	
I. A maximum extended in-house or follow-up period cannot be pre-defined as the extension will be as long as necessary to ensure the safety of the individual participant(s).
 
II. The maximum extended in-house or follow-up period for study treatment groups will be based on evolving safety, tolerability and PK data and will not usually exceed 5x human $t_{1/2}$ of UPB-101.
 
III. Alterations in duration of in-house stay or follow-up need to ensure that sufficient data are obtained to fulfil the study objectives and be a reflection of the established safety and tolerability PK profile

Screening	
1. Screening assessments, including Holter ECG recordings, performed at Richmond Pharmacology Ltd (RPL) on participants screened (but not randomized) for another study can be used for this study to avoid unnecessary tests.
 
2. Screening assessments performed prior to signing the ICF for this study at RPL on volunteers screened (but not randomized) for another study or screening for a generic protocol can be used for this study to avoid unnecessary tests/repeats.
	
I. The assessments must meet protocol criteria (e.g., the method to be used).
 
II. The assessments (except Holter ECG recordings) must be performed within the protocol defined Screening window (Day -21 to -2).
 
III. Holter ECG recordings performed either under this or another approved clinical study protocol and informed consent are valid for a period of three months before Day -2.

Adaptive Study Design Areas	Features	Limits
ECG analysis	
1. All ECGs will be assessed for safety by the Investigator and will be transferred to the central ECG laboratory.2. ECGs from timepoints on Day 22, Day 43, Day 57 and Day 71 will be stored at the central ECG laboratory but not adjudicated unless requested by the Sponsor.3. ECGs from all other timepoints will be adjudicated and the output from the adjudication will be included in the CSR.	
I. There will be comprehensive collection of ECGs (in triplicate), time matched to PK assessments, throughout the study.II. If a safety issue occurs that necessitates the adjudication of ECG data from the timepoints listed in (Features no. 2), this analysis will be performed and will be reported in the CSR.III. If adjudication of ECGs from the timepoints listed in (Features no. 2) is requested by the Sponsor for another reason, this analysis will be performed and may or may not be reported in the CSR.
Post-dose telemetry	
1. Continuous 12-lead telemetry will be monitored and recorded from at least 1-hour pre-dose to 24 hours post-dose	
I. Post-dose telemetry data will be stored and can be optionally analyzed and reviewed by cardiologist in case of clinically significant AE and/or be used to provide additional information for more extensive optional cardiac assessments, or in any other circumstances where analysis may be beneficial.II. The results of assessments performed in case of a clinically significant AE will be reported in the CSR. The results of any other optional assessments may or may not be reported as part of this study.

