2.2.2 Secondary

- The safety endpoints will include AEs, SAEs, physical examinations, clinical laboratory assessments, vital signs, electrocardiograms (ECGs) including telemetry, withdrawal of participants, and early terminations. These endpoints will be assessed from baseline through Day 85 ± 5 days in the Safety Set.
- The immunogenicity endpoint includes UPB-101 anti-drug antibodies (ADAs) and presence of neutralizing antibodies (Nabs). These endpoints will be assessed from baseline through Day 85 ± 5 days in the Immunogenicity Set.

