### 4.10.6 Electrocardiograms

TriPLICATE ECGs are performed at each timepoint ensuring the following criteria:

- Three consecutive evaluable ECGs;
- With maximum HR of 2 bpm difference;
- TriPLICATE is obtained between 1.5 to 4.5 minutes.

Due to above criteria, up to 10 ECGs can be acquired for a given timepoint. Typically, in most cases, the last 3 ECGs represent the triPLICATE which will be transferred to Clario for adjudication. If a triPLICATE could not be obtained (e.g. due to variable heart rate) then the last 3 ECGs are transferred for adjudication.

Adjudicated ECGs (Clario) will be used for analyses in the TFLs. Un-adjudicated ECGs (internal RPL) will be listed only. Details are as below.

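### Table 6 allows a sponsor-requested central ECG reading, or an optional telemetry analysis, to be carried out and then left out of the CSR

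*Protocol*

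**What the plan says.** Protocol Section 2.2.2 makes the secondary safety endpoint include "electrocardiograms (ECGs) including telemetry, withdrawal of participants, and early terminations", assessed from baseline through Day 85.

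Table 6 (Protocol Section 3.4), ECG analysis row, sets three different rules for central adjudication:

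- ECGs from Days 22, 43, 57 and 71 "will be stored at the central ECG laboratory but not adjudicated unless requested by the Sponsor".
- If a safety issue makes adjudication of those visits necessary (limit II), "this analysis will be performed and will be reported in the CSR".
- If adjudication of those visits "is requested by the Sponsor for another reason" (limit III), "this analysis will be performed and may or may not be reported in the CSR".

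For the remaining visits there is no discretion: "ECGs from all other timepoints will be adjudicated and the output from the adjudication will be included in the CSR".

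The post-dose telemetry row follows the same pattern. Under limit II, assessments made because of a clinically significant adverse event must go into the CSR, and then: "The results of any other optional assessments may or may not be reported as part of this study".

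SAP 4.10.6 states that "Adjudicated ECGs (Clario) will be used for analyses in the TFLs" and that un-adjudicated ECGs are only listed.

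**The concern.** Leaving four visits unadjudicated by default is a legitimate choice made in advance. The difficulty is the permission not to report a reading or analysis after it has been performed. No section requires the reporting decision to be made before the result is seen, gives criteria for it, or says what separates a safety issue under limit II from another reason under limit III.

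At stake is the completeness of the ECG safety summary. Because the SAP tabulates adjudicated ECGs only, a request under limit III is the one route, without a safety trigger, by which these visits can reach the QTcF tables. Reporting that can depend on the result can make that summary look cleaner than the data.

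**Working it through.** The plan states no figure on this point, so there is none to reproduce. The check is a comparison of the texts plus a count of how much of the endpoint is affected.

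**1. The texts side by side**

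| Place | What it implies for an adjudicated Day 22, 43, 57 or 71 ECG requested for a non-safety reason |
|---|---|
| Protocol Table 6, ECG limit III | Analysis is done; reporting in the CSR is optional |
| Protocol 7.8.3 | Adjudication results go to the site and into the study database |
| SAP 4.1 | All collected data appear in by-subject listings |
| SAP 4.10.6 | Adjudicated parameters are listed separately; all ECG summaries and QTcF categories use adjudicated ECGs |

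The last three rows point towards the result being stored, listed and tabulated. The first says it need not be reported. The SAP does not mention these four visits or Table 6, and SAP 4.15, which records departures from the protocol analysis, is silent on the matter. The question is left open.

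For telemetry, SAP 4.10.4 lists start and end times and the evaluation. It has no rule for an additional telemetry analysis, so Table 6 telemetry limit II stands alone.

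**2. How many timepoints are affected (12-lead ECG column of Protocol Table 5)**

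- Day 1: 10 timepoints (−2, −1, −0.5, 0.5, 1, 4, 5, 6, 7 and 8 h), of which 3 are pre-dose.
- Days 2 to 15: 14 timepoints.
- Follow-up: 6 visits (Days 22, 29, 43, 57, 71 and 85).
- Total 10 + 14 + 6 = 30; post-dose 30 − 3 = 27.

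Discretionary visits:

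- 4/30 = 13.3% of all timepoints in Table 5
- 4/27 = 14.8% of post-dose timepoints
- 4/6 = 66.7% of follow-up visits

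With the planned 32 participants all attending and three tracings per timepoint:

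- 4 × 32 = 128 participant-visits
- 128 × 3 = 384 tracings, out of 30 × 32 × 3 = 2,880

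After discharge, only Days 29 and 85 have adjudication and reporting that do not depend on a request.

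**3. What can and cannot be omitted**

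- Cannot be omitted: the un-adjudicated intervals and overall evaluation for every visit (Protocol 10.5, SAP 4.10.6), the telemetry evaluation (SAP 4.10.4), any adjudication necessitated by a safety issue, and any telemetry assessment made for a clinically significant adverse event.
- Can be omitted: the central reading requested for another reason, and any other optional telemetry analysis.

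**The case against.** The strongest reply is that nothing relevant to safety is hidden. The investigator reviews every ECG, un-adjudicated values are listed with flags and clinical relevance, telemetry is monitored in real time and its evaluation listed, and the two safety-driven routes carry mandatory reporting. Protocol 7.8.3 with SAP 4.1 and 4.10.6 would, read together, have an adjudicated result listed anyway. The ECG endpoint requires assessment, not central adjudication, and safety is purely descriptive, so no planned estimate is biased.

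Most of this stands, and it rules out several stronger readings that a reader might infer:

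- *That ECG safety findings can be suppressed.* The underlying record is listed; only the central re-read or extra analysis is optional.
- *That protocol and SAP contradict each other outright.* The SAP does not address these visits specifically, so the texts are unreconciled rather than opposed.
- *That the open-label design creates the problem.* Whoever commissions a re-read sees the result with or without blinding, so this adds little.
- *That the sponsor is named as deciding what is reported.* Table 6 names no one. The sponsor's role is inferred from its right to request adjudication and its general approval of adaptive features, and the inference is weaker for telemetry.
- *That a number of concealed QTcF values can be estimated.* The documents give no event rate. An assumed rate would give the chance that such values occur, not the chance that a reading is requested and then withheld.

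The reply does not remove the permission itself. The general SAP rules do not cancel limit III, and listed un-adjudicated values do not show whether a central reading was made and left out.

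**Conclusion.** The point holds in a limited form. Table 6 permits an analysis already performed on part of a descriptive secondary safety endpoint to be omitted from the CSR. For ECGs this concerns 4 of 30 timepoints in Table 5, or 4 of 6 follow-up visits, and only the centrally adjudicated reading. For telemetry it concerns any assessment not prompted by a clinically significant adverse event. The permission can allow selective reporting; the documents do not show that it was used or intended. The consequence is that whether these visits enter the QTcF tables may rest on a choice made after the reading is known. The timepoint count comes directly from Table 5; the tracing count assumes full attendance and exactly three tracings per timepoint. This is a modest defect, worth correcting because correction is cheap.

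**What to change.** In Table 6, ECG analysis limit III and post-dose telemetry limit II, replace the optional clause with a commitment that the result will be reported in the CSR together with the reason for the request. Limit II of the ECG row already contains the required commitment and can serve as the model.

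SAP 4.15 refers to study completion, so amending Table 6 may no longer be practical. In that case add to SAP 4.10.4 and 4.10.6 that:

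- every ECG adjudication and telemetry analysis performed before database lock will be listed;
- adjudicated ECGs from these visits will be included in the summaries;
- if no such adjudication or analysis was done, the CSR will say so.

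The cost is two changed clauses or a short SAP addition, and a few more table or listing rows if the option is used. The sponsor keeps its right to request any analysis and loses only the option to leave it out of the CSR. No clinical procedure changes.

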3.5 Rationale for study design and dose of UPB-101

This study is designed for the purpose to increase understanding of the clinical profile of UPB-101.

The rationale for investigating a possible difference in the PK of UPB-101 attributable to the Japanese ethnicity is to determine the optimal dose and dosing frequency of UPB-101 in this specific population, which due to genetic differences may be different to that of other ethnicities. 24 Japanese participants (8 participants across 3 treatment groups) and 8 NJNAE participants is sufficient to explore this objective. The NJNEA treatment group will aim to include Caucasian and 2-3 non-Caucasian participants to ensure diversity. They must also be 'non-East-Asian' (i.e., not Chinese, Korean, Mongolian or Taiwanese), as there may be genetic overlap between Japanese and East-Asian participants.

The study will be open label.

Nonclinical and clinical studies have shown no safety concerns for UPB-101 administered in doses significantly higher than the maximum planned dose for this study (█ mg). Therefore, sentinel or ascending dosing is not required. There are also no adaptive features which allow for doses that exceed the maximum planned dose of █ mg, which is well within the safe range of doses already tolerated in the FIH study. As a result, there are no dose escalation rules or dosing decisions to be made between cohorts; therefore, there is no need for an interim SRC review.

All treatment groups will enrol and dose in parallel. On Day 1, Japanese members of the cohort will be randomized to either treatment group 1, 2 or 3, and NJNEA participants will automatically be assigned to treatment group 4. The study will be completed in as few cohorts as operationally possible to minimize period bias. Attempts will be made to include in each cohort at least 2 participants assigned to each of the 4 treatment groups (therefore a minimum of 8 participants per cohort and a maximum of 4 cohorts to complete the study).

Safety will be monitored on an on-going basis by the investigator and medical monitor including vital signs, laboratory and urine tests, physical examination, AEs and injection site monitoring. The predicted exposures for the highest planned dose (█ mg) are comfortably below those already found to be safe and well-tolerated in humans; therefore, there are no anticipated ADRs or clinical laboratory abnormalities. At the Investigator and Sponsor discretion, any safety concerns identified during the study may result in suspension of enrolment at that dose level pending safety review and outcome of an *ad hoc* SRC (Section 4.2). Dosing at lower levels may continue, if permitted in line with the study specific AR rules (Section 4.3). Should the clinical study be suspended because of any safety concern, the study restart will only be possible after receipt of written regulatory authority approval via a substantial Clinical Trial Application amendment (with or without a protocol modification required by the SRC or Sponsor).

The safety, tolerability, PK, and immunogenicity of a single ascending dose in NJNEA adults have already been characterized in clinical study 7266-CL-0001. Safety, tolerability, immunogenicity and PK assessments will be conducted at specified intervals during this study which bracket the $t_{1/2}$ (median = █ days) and time to maximum concentration (t_{max}) (█) observed in study 7266-CL-0001 for a single dose of █ mg/kg UPB-101 administered subcutaneously.

3.5.1 Justification for the selected dose level

In the nonclinical 26-week repeat dose toxicity study in cynomolgus monkeys, the NOAEL was determined as █ mg/kg for both male and female monkeys. The HED for this NOAEL level is █ mg/kg or a dose of █ mg, assuming a 70 kg human (HED calculation according to guideline (FDA 2005)). Thus, the highest dose of █ mg to be used in this study is 7.5-fold lower than the HED NOAEL dose determined in nonclinical toxicity studies.

UPB-101 has been administered as a single IV dose from █ mg to █ mg (█ mg/kg; assuming a 70 kg human) and as a single SC dose of █ mg (█ mg/kg; assuming a 70 kg human) to healthy male and female non-Japanese participants and was considered safe and well-tolerated (Study 7266-CL-0001). PK analysis found that area under the concentration-time curve from the time of dosing extrapolated to time infinity (AUC_{0-inf}) and C_{max} in that study

increased dose proportionally. At the highest dose tested (█ mg/kg), C_{max} and AUC_{0-inf} after a single IV administration were █ $\mu\text{g/mL}$ and █ days· $\mu\text{g/mL}$, respectively. Bioavailability after SC administration was █. SC dosing was chosen for further development since this has significant benefits including potential self-administration.

PK modelling was performed based on the IV and SC data from Study 7266CL-0001. A two-compartment linear PK model was fitted to the mean data after single SC administration of █ mg/kg UPB-101 (Study 7266-CL-000).

The proposed study will explore SC doses in the █ mg range. These doses are all significantly below the maximum dose (█ mg/kg IV) administered in the completed SAD study (above and Section 1.1) and there is a significant margin of safety with regard to exposure at doses which have previously been shown to be safe and well-tolerated.

Table 7 lists the model-projected exposures following a single █ mg SC injection in comparison to the maximal exposure that was found safe and well tolerated in the SAD study (Study 7266-CL-000). The predicted maximal C_{max} and AUC_{0-inf} for a single SC injection in this study (at the highest dose of █ mg SC) are █ and █, respectively, when compared with the observed C_{max} and AUC_{0-inf} following administration of █ mg/kg IV in Study 7266-CL-0001, a dose that was found to be safe and well tolerated.

This data provides the rationale for the randomized treatment group design. For all treatment groups, the projected single-dose exposures are lower than the exposures that were found to be safe and well tolerated in Study 7266-CL-0001.

Table 7: Predicted mean PK parameters after single SC administration UPB-101 compared to the maximal IV dose of completed study 7266-CL-0001

Route	Single Dose				Fraction of Maximal SAD Exposure	
	Dose (mg)	Dose (mg/kg)	C_{max} ($\mu\text{g/mL}$)	AUC_{0-inf} (days· $\mu\text{g/mL}$)	C_{max} IV/ C_{max} SC	AUC_{0-inf} IV/ AUC_{0-inf} SC
SC	█	█	█	█	█	█
SC	█	█	█	█	█	█
SC	█	█	█	█	█	█
SC	█	█	█	█	█	█
IV	█	█	█	█		

Abbreviations: AUC_{0-inf} =area under the concentration-time curve from the time of dosing extrapolated to time infinity; C_{max} =maximum observed serum concentration; IV=intravenous; PK=pharmacokinetic; SAD=single ascending dose; SC=subcutaneous.

The doses selected for this study (i.e., █ mg, █ mg, and █ mg) were informed by the PK and PK/PD data derived from the SAD study in healthy adult male and female volunteers. All three doses resulted in serum concentrations of UPB-101 that remained above the therapeutic threshold (█ for at least █ and are, therefore, candidates for future drug development.

Consequently, these same three doses are being administered to asthmatic participants in the ongoing MAD study. The results from this Japanese ethno-bridging study and the MAD study will help determine the optimal dose and dosing frequency (based on safety, tolerability, PD, immunogenicity, and PK) to be applied to future clinical studies.

